BioNTech SE Confidential	Clinical Trial Protocol BNT162-14	Page 7 of 91 Version: 4.0 Date: 20, IAN 2022
		Date: 20 JAN 2022

Trial population

This trial will enroll subjects aged \geq 18 years who received one or two previous injections of a BNT162 candidate vaccine in either the BNT162-01 trial or the BNT162-04 trial. Volunteers will not be enrolled if they have received any COVID-19 vaccine outside of the BNT162-01 trial or the BNT162-04 trial.

The maximum number of trial subjects in the Group A (BNT162-01 trial subjects in Cohorts 1 to 14 who received 2 x Comirnaty 30 μ g) will be 90 and in Group B (all other BNT162-01 or BNT162-04 trial subjects) will be 459. A subset of Group B (n = 129) will be asked to participate in an immunologic subset evaluation.

Trial treatments

IMP name:	BNT162b2 (Comirnaty) or BNT162b2s01.					
Туре:	Vaccine (BNT162 RNA-LNP vaccine utilizing modRNA).					
Administration route:	Intramuscular (IM); upper arm, musculus deltoideus. The same arm may be used for both immunizations. The non-dominant arm is preferred.					
Dosing regimen:	Group A: One (at Day 1) IM injection with 30 µg of either Comirnaty or BNT162b2s01.					
	Group B: Two (at Day 1 and Day 21) IM injections with 30 µg of Comirnaty, except Group B transplant subjects.					
	Group B transplant subjects: Two IM injections of 30 µg of Comirnaty, with injection 2 administered 3 to 7 months after injection 1 (Day 1).					
	The planned time points for injection of IMP for Groups A and B are provided in the SoA (Section 1.3).					
Sourcing:	Provided centrally by the sponsor.					
Packaging and labeling:	IMP will be provided in glass vials as open-label supply. Each vial will be labeled as required per country requirements. For details, see the Pharmacy Manual.					

BioNTech SE	Clinical Trial Dratacal	Page 8 of 91		
		Version: 4.0		
Confidential	BINT 102-14	Date: 20 JAN 2022		

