- k For subjects who receive non-trial SARS-CoV-2 vaccinations there will be no sampling in subsequent visits. Information about these vaccinations may be received outside of a planned visit and can be collected remotely, e.g., by phone. In such cases information on physical examination and vital signs can be skipped. However, AEs that occurred prior to administration of non-trial vaccine must be enquired and should be recorded as stated in footnote "i".
- Record any non-trial SARS-CoV-2 vaccinations that trial subjects receive during the trial in the CRF until the last trial visit.

Abbreviations: AE = adverse event; AESI = adverse event of special interest; CMI = cell mediated immunity; CRF = case report form; d = day; ELISA = enzyme-linked immunosorbent assay; EOT = end of trial; h = hour(s); IMP = investigational medicinal product; inj. = (IMP) injection; NAAT = nucleic acid amplification-based test; NATAB = neutralizing antibody titers and antibody binding; SAE = serious adverse event; SARS-CoV-2 = the virus leading to COVID-19; SoA = schedule of activities; WOCBP = women of childbearing potential.

		Page 12
BioNTech SE	Clinical Trial Protocol	Versio
Confidential	BNIT162 14	VEISIO
Connuential	DINT 102-14	Dete: 00 I

Page 12 of 91 Version: 4.0 Date: 20 JAN 2022

Table 2: Schedule of events for Immunology Subgroup of Group B (with two injections of Comirnaty) h

Activity	Visit 0	Visit 1	Visit 2	Visit 3	Visit 4	Visit 5	Visit 6 ^{I, m}	Visit 7 ^{I, m, o}	Early termination
Week(s)			1	3	4	7	12	26	
Day	-30 to -1	1	8+2	22±3	29+7	50±7	85±10	182±20	
	(Screening)	(Day of inj. 1; pre-dose except IMP injection)	(~7 d post inj. 1)	(~21 d post inj. 1; pre-dose except IMP injection)	(~7 d post inj. 2)	(~28 d post inj. 2)	(~63 d post inj. 2)	(~161 d post inj. 2 EOT Visit)	
Collect informed consent	Х						X m	X m	
Assess inclusion/exclusion criteria compliance	Х	X (review)							
Collect demographic and medical history	Х	X (update)							
Physical examination	Х	X a	X a	X a	X a			X a	X a
Vital signs, body weight ^b	Х	Хc		Хc					
Urine pregnancy test for WOCBP	Х	х		х				х	х
Blood draw for clinical laboratory (15 mL) ^d	Х								
Allocation to IMP		х							
IMP injection, then observe subjects for ~1 h		х		X ^h					
Subject hotline availability	Start	=>	=>	=>	=>	=>	=>	End	(End)
Oral swabs for NAAT-based SARS-CoV-2 for screening ^f	X e	X e							
Oral swab for NAAT-based SARS-CoV-2 testing for surveillance			х	x	х	Х	х	х	x

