6.4. Primary endpoint analyses

The primary endpoints are solicited local reactions at the injection site occurring up to 7 days after each injection, solicited systemic reactions occurring up to 7 days after each injection, the proportion of subjects with at least one serious adverse event (SAE) occurring up to 26 weeks after the first injection, the proportion of subjects with at least one adverse event of special interest (AESI) occurring up to 26 weeks after the first injection and the proportion of subjects with at least one unsolicited treatment emergent adverse event (TEAE) occurring up to 28 days after each injection.

All primary analyses will be performed using the SAF and analyses of adverse events for Group B will possibly be repeated using the SAFB.

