6.4.3. Adverse events

Definition

For detailed information on adverse events see Section 10.3 of the protocol. Solicited AEs that are recorded from the subject diaries on the reactogenicity CRFs will not be reported as AEs unless the solicited AE meets criteria for SAE or begins after Day 8 or started before Day 8 and continues past Day 8.

Adverse events (AEs) will be coded using the Version MedDRA[®] 24.0 to get a system organ class (SOC) and preferred term (PT) for each AE.

A TEAE is defined as any AE with an onset after the first injection (Dose 1) (if the AE was absent before the first injection) or worsened after the first injection (Dose 1) (if the AE was present before the first injection (Dose 1)). AEs with an onset date more than 28 days after the last injection will be considered as treatment emergent only if

assessed as related to IMP by the investigator. AEs that cannot be determined to not be treatment emergent due to missing date or time will be defined as TEAE.

Note: To clarify the definition in the protocol, AEs with an onset date at the date of the first injection (Dose 1) will only be considered as treatment emergent if the AE occurred after the first injection (Dose 1). AEs with missing time and occurring on the day of Dose 1 or AEs with missing date will be analyzed as treatment emergent.

TEAEs will be evaluated for following time interval and groups:

- Up to 28 days after the first IMP injection (Group A and immunology subset of Group B)
- After the first IMP injection up to 28 days after the second IMP injection (immunology subset of Group B non-transplant)
- After the second IMP up to 28 days after the second IMP injection (immunology subset of Group B transplant)
- All TEAEs (Group A and immunology subset of Group B)

AEs are assigned to the time interval according to their start date and time. AEs with missing date will be assigned to each of the respective intervals if it cannot be ruled out, that it belongs to the time interval.

Adverse events of special interest (AESIs)

The following events will be reported as AESIs: myocarditis, pericarditis, anaphylaxis, thromboembolic events (e.g., deep vein thrombosis, stroke, myocardial infarction), immune thrombocytopenia and immune based neurologic events (e.g., optic neuropathy, Guillain-Barré syndrome). AESIs are recorded in the CRF.

AESIs and SAEs will be evaluated up to 26 weeks after the ICF was signed for all groups.

Analysis

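### In the non-transplant Group B immunology subset, the 28-day TEAE interval after injection 1 normally runs about 7 days past injection 2, and no interval isolates TEAEs after injection 2

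*SAP*

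**What the plan says.** SAP 6.4 words this primary endpoint as the share of subjects who have any "unsolicited treatment emergent adverse event (TEAE) occurring up to 28 days after each injection".

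SAP 6.4.3 then lists four intervals for the evaluation:

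- One for the first injection: "Up to 28 days after the first IMP injection (Group A and immunology subset of Group B"), with no exception for non-transplant subjects and no cut at injection 2.
- One that is cumulative over both injections: "After the first IMP injection up to 28 days after the second IMP injection (immunology subset of Group B non-transplant"). For these subjects no other interval with a time limit is listed.
- One for injection 2 alone, which only the transplant subjects have: "After the second IMP up to 28 days after the second IMP injection (immunology subset of Group B transplant").
- A last one without a time limit, which takes in every TEAE.

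The allocation rule is "AEs are assigned to the time interval according to their start date and time". It does not consider which injection last preceded the event.

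On timing, Protocol Table 2 (Section 1.3) places injection 2 for non-transplant subjects at Visit 3, Day 22±3, described as "21 d post inj. 1; pre-dose except IMP injection". The dosing text in Protocol 1.1 says "Two (at Day 1 and Day 21) IM injections". Transplant subjects follow a different schedule, "with injection 2 administered 3 to 7 months after injection 1 (Day 1").

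**The concern.** An interval named for the first injection should describe what happens after the first injection. In non-transplant subjects of the immunology subset, it also covers the opening days after the second. Lymphadenopathy is a realistic example: Protocol 8.5 names it as an adverse reaction, and it is not on the diary list in Protocol 8.2.4. With onset on Day 24, two days after injection 2, it would be counted under the first-injection label.

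The same label then means different things in different columns. Group A has one injection. Transplant subjects have had one injection by Day 29. Non-transplant subjects have normally had two. SAP 6.1.1 also calls for a total column over the immunology subset, which pools the last two.

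At stake is whether a primary safety endpoint can be read per injection in this subset.

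**Working it through.** **Inputs.** Interval definitions and the allocation rule: SAP 6.4.3. Visit days: Protocol Table 2. Subset counts: Protocol 4.1.

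**The protocol's own figure.** Table 2 labels Visit 4 (Day 29) as about 7 days after injection 2. Day 29 − Day 22 = 7, so this is reproduced. Day 22 − Day 1 = 21 days between injections also agrees.

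**Subjects affected.** 36 + 30 + 15 + 48 = 129 in the immunology subset. Less 15 transplant subjects, this leaves 114. The remaining non-transplant Group B subjects, 459 − 129 = 330 at most, are outside these TEAE intervals. Table 3 records only AESIs, SAEs and COVID-19-linked AEs for them.

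**Overlap.** The interval ends 28 days after Day 1, on Day 29. Overlap = 29 − (day of injection 2); share = overlap / 28.

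| Injection 2 on | Days after injection 2 inside the interval | Share of 28 days |
|---|---|---|
| Day 19 | 10 | 36% |
| Day 21 (dosing text) | 8 | 29% |
| Day 22 | 7 | 25% |
| Day 25 | 4 | 14% |
| Day 29 or later, or not given | 0 | 0% |

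If the window is counted as study days 1 to 28, as the SAP counts its solicited intervals, Days 22 to 28 are still 7 calendar days.

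**Can the other intervals recover injection 2?** With injection 2 on Day 22, the cumulative interval ends on Day 22 + 28 = Day 50. Removing the first interval from it leaves Days 29 to 50, which is 21 of the 28 days after injection 2 and omits the first 7. Subject-level proportions cannot be subtracted in any case, because one subject may have events in both parts.

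**Where it reaches output.** In SAP 6.4.3 the worst-grade TEAE tables are expressly by time interval. The overall summary and the SOC/PT tables name no interval.

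**Size of any excess (assumptions only).** Neither calculation below uses rates from the documents.

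- *Events, against a single-injection group.* Let the daily rate in the week after any injection be k times the later rate. The count ratio over 28 days is (14k + 14) / (7k + 21) = 1.00, 1.20 and 1.33 for k = 1, 2 and 3. The share of events after injection 2 is 7k / (14k + 14) = 25%, 33% and 37.5%.
- *Subjects, against an interval cut at injection 2.* Let a be the risk in the 21 days after injection 1 and b the risk in the 7 days after injection 2, taken as independent. The interval as written shows 1 − (1 − a)(1 − b), an excess of (1 − a)b. For a from 10% to 30% and b from 5% to 20%, it shows 14.5% to 44.0% against 10% to 30%. The excess runs from 0.70 × 0.05 × 114 = 4 subjects to 0.90 × 0.20 × 114 = 21 subjects. Part of it simply reflects 28 days being compared with 21.

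**The case against.** The best defence is that the endpoint need not be per injection. The objectives tables (Protocol Section 3, SAP Table 2) say only that TEAEs are counted up to 28 days after IMP injection, whereas for solicited reactions they specify each injection. With injections three weeks apart, a window over the whole regimen is reasonable, and the cumulative interval supplies it. The label of the first interval is literally true of a Day 24 event. The trial is descriptive, and Group B is neither randomized nor formally compared with Group A.

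Much of this stands as a limit on the point, and it rules out several stronger readings that a reader might infer:

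- *That events are lost or mislabelled as Dose 1 results.* They also enter the cumulative and all-TEAE intervals, and the SAP uses no such label.
- *That the first-injection proportion is inflated by a known amount.* With a constant daily rate (k = 1), the expected event count equals that of a single-injection group. Any excess over such a group needs a first-week peak, for which the documents give no rate. Diary-solicited reactions mostly stay out of the TEAE tables, which weakens the case for a peak, although the Day 8 rule for them is not clearly tied to a dose.
- *That all of non-transplant Group B is affected.* Only the immunology subset is.
- *That a subject who never receives injection 2 drops out of every interval.* TEAEs within 28 days of injection 1 fall in the first interval, and all of them fall in the all-TEAE interval. SAP 6.1.1 also allows some Group B AE analyses to be repeated in the two-dose safety set. What remains is a cumulative interval with no defined end for that subject.

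The defence does not remove the core. SAP 6.4 says each injection. SAP 6.4.1 and 6.4.2 give the whole immunology subset separate injection 2 intervals for solicited reactions, and SAP 6.4.3 gives transplant subjects one for TEAEs. Even on a regimen-level reading, the first interval in non-transplant subjects describes neither one injection nor the full regimen.

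**Conclusion.** The point holds for the planned 114 non-transplant subjects of the immunology subset. With injection 2 on schedule, about 7 of the 28 days (25%; 14% to 36% across the visit window) in their only first-injection interval follow injection 2, and no listed interval isolates TEAEs after injection 2. This rests on nominal timing. Protocol 7.1.2 permits medical delays, and the overlap disappears if injection 2 falls at least 7 days after Day 22 or is not given.

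The consequence is one of interpretation: the by-interval worst-grade tables mix exposures, and the endpoint as worded in SAP 6.4 cannot be read from the intervals for these subjects. The direction and size of any difference from Group A cannot be derived from the documents. The undefined end of the cumulative interval for a subject without injection 2 is a minor wording gap.

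**What to change.** In SAP 6.4.3, for non-transplant subjects of the immunology subset:

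1. End the first interval at the date and time of injection 2, or at 28 days after injection 1, whichever is earlier.
2. Add an interval from injection 2 to 28 days after it, matching the one already given for transplant subjects.
3. Footnote that the first interval is about 21 days in this subset (18 to 24 across Day 22±3), so its proportions differ in observation time from those of Group A and the transplant subjects.
4. As a minor clarification, end the cumulative interval at 28 days after the last injection received.

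The Day 21 dosing text and the Day 22±3 schedule in the protocol must also be reconciled.

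No new data are needed. Protocol 6.4 already requires the date and time of each injection in the CRF, and SAP 6.1.2 already derives the days from the last injection to AE onset. The work is SAP wording, one cut date and one extra interval in the programs. The price is a shorter first window, which the footnote discloses.

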	Group B immunology subset and will receive one injection of Comirnaty [®] which could be potentially followed 3 to 7 months afterwards by a second injection of Comirnaty [®] . This group will be referred to as Group B transplants. Subjects not eligible during this period due to any medical reason (e.g., breakthrough infection causing investigational medicinal product delay decision from the investigator) will not receive the 4 th dose in this trial. Dose : 30 µg of Comirnaty [®] or BNT162b2s01 Dosing regimen: Group A: One (at Day 1) intramuscular injection with 30 µg of either Comirnaty or BNT162b2s01. Group B: Two (at Day 1 and Day 21) intramuscular injections with 30 µg of Comirnaty, except Group B transplant subjects. Group B transplant subjects: Two intramuscular injections of 30 µg of Comirnaty, with injection 2 administered 3 to 7 months after injection 1 (Day 1). The planned time points for injection of the investigational medicinal product for Groups A and B are provided in the Schedule of Activities in the protocol (Section 1.3)
	Administration route: Intramuscular
Treatment and study duration	In total, the planned trial duration for a subject in this trial is approximately 30 weeks (≤4 weeks of screening and ~26 weeks follow-up).
Planned number of subjects	The maximum number of subjects in Group A will be 90 (including up to 15 HIV-positive subjects) and in Group B will be 459 (including up to15 transplant subjects). A subset of Group B (n=129) will be asked to participate in an immunology subset evaluation.
Randomization and blinding	Subjects in Group A will be randomized in a 2:1 ratio to either BNT162b2s01 or Comirnaty [®] . All subjects in Group B will receive at least one injection of Comirnaty [®] . They will not be randomized. The study is open-label.

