5.1. Definition of analysis sets

Screened set (SCR)

The screened set is defined as all subjects who signed informed consent.

Safety set (SAF)

The safety set is defined as all subjects who received at least one dose of investigational medicinal product (IMP).

Safety boost set (SAFB)

The safety boost set is defined as all subjects who received two doses of IMP (first injection (Dose 1) and second injection (Dose 2)).

Note: Group A will be excluded from the SAFB as they receive only a single injection according to protocol.

Immunogenicity set (IMM)

The immunogenicity set is defined as all subjects who received at least one dose of IMP and have at least one post-baseline functional antibody titer (e.g., VNT or an equivalent assay) immunogenicity assessment.

Note: The expression 'have at least one post-baseline functional antibody titer immunogenicity assessment' refers to having either at least one post-baseline neutralizing antibody titer or one post-baseline ELISA titer immunogenicity assessment.

Immunogenicity per-protocol set (IMMPP)

The immunogenicity per-protocol set is defined as all subjects included in the immunogenicity set that have no major protocol deviations as determined by the clinician and who received two doses of IMP (first injection (Dose 1) (for Group A and B) and second injection (Dose 2) (only for Group B)).

Note: Subjects with any major protocol deviation thought to interfere with either the mechanism of action or immunogenicity test measurements will be excluded from IMMPP set.

Note: The definitions of all analysis sets apply within the BNT162-14 trial. In all analysis sets, subjects will be assigned to the treatment groups (i.e., vaccine type) according to the actual treatment they received ("as treated"). The condition of receiving two doses of IMP will not apply to Group A.

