6.1.1. Tables and listings

Tables

In general, data will be summarized as follows:

- Group A by vaccine [Comirnaty[®], BNT162b2s01], and total
- Group A subjects having received Comirnaty[®] by HIV infection status
- Group A subjects having received BNT162b2s01 by HIV infection status
- Group B by transplant status, and total
- Group B immunology subset by transplant status, and total

Descriptive summary tables and figures will be based on scheduled visits.

Continuous variables will be summarized using the following descriptive statistics: number of subjects with non-missing data (n), mean, standard deviation (SD), median, minimum (min) and maximum (max).

Descriptive statistics of titer and fold rise of titer will additionally include geometric mean and its two-sided 95% confidence interval (CI). The geometric mean titer (GMT) is calculated as the mean of the logarithm of the functional antibody titers, backtransformed into the original scale. Two-sided CIs will be obtained by calculating CIs using t-distribution for the mean of the logarithmically transformed assay results and transforming the limits back to the original scale.

Geometric mean fold rise (GMFR) is calculated as the mean of the difference of logarithmically transformed assay results (post vaccination time point – pre vaccination time point) and back-transformed into the original scale. Two-sided CIs will be obtained by calculating CIs using Student's t-distribution for the mean difference of the

logarithmically transformed assay results and transforming the limits back to the original scale.

Categorical variables will be summarized presenting absolute and relative frequencies (n and %) of subjects in each category (including the category 'missing' if applicable). Percentages will be calculated based on the number of subjects in the respective analysis set (N) as denominator if not stated differently. Percentages may be presented with exact 95% Clopper-Pearson CIs.

SDs and CIs will only be calculated if values from at least 3 subjects are available.

Listings

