Important Case Report Form (CRF) data and all relevant generated and transformed variables together with the original data items will be listed. Separate listings will be provided for Group A and B and immunology subset of Group B. Listings will be sorted first by vaccine (for Group A), subgroup (HIV-positive subjects for Group A, transplant subjects for Group B or immunology subset of Group B), site ID and by subject number and finally, if applicable, by visit number and/or a relevant date (e.g., date of onset of AE).

Programming

SAS[®] (version 9.4 or higher) programming will be performed according to Staburo GmbH standards as defined in SOP001_PROGRAMMING [1] and related work instructions. Special attention will be paid to planning and performance of quality control measures as documented in the quality control plan for the analysis of this study (see also SOP002_PROGRAM_QC [2]).

Analysis sets

The SCR will be used for disposition. The SAF will be used for analysis of safety and adverse events data. Some analyses of the adverse events will be repeated for Group B using the SAFB if the SAF and the SAFB sets differ. The IMM will be used for the analysis of immunogenicity data. The immunogenicity analyses may be repeated using the IMMPP if the two analysis sets differ significantly. This will be decided at the data review meeting.

Data of subjects who failed to complete all visits of the trial (dropout or withdrawal) will be reported as far as their data is available.

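### The transplant TEAE interval that starts at Dose 2 takes the one-dose safety set as its default denominator, so its percentage is understated if any transplant subject misses Dose 2

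*SAP*

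**What the plan says.** SAP 6.4 counts among the primary endpoints the "proportion of subjects with at least one unsolicited treatment emergent adverse event (TEAE) occurring up to 28 days after each injection". SAP 6.4.3 then sets the intervals. For non-transplant subjects the interval that covers the second injection opens at the first: "After the first IMP injection up to 28 days after the second IMP injection (immunology subset of Group B non-transplant". For transplant subjects it opens at the second: "After the second IMP up to 28 days after the second IMP injection (immunology subset of Group B transplant".

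Three statements together determine the denominator:

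- SAP 6.4: "All primary analyses will be performed using the SAF and analyses of adverse events for Group B will possibly be repeated using the SAFB".
- SAP 5.1: "The safety set is defined as all subjects who received at least one dose of investigational medicinal product (IMP".
- SAP 6.1.1: "Percentages will be calculated based on the number of subjects in the respective analysis set (N) as denominator if not stated differently".

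Section 6.4.3 gives no separate denominator for adverse events. On the SAFB, which SAP 5.1 restricts to subjects with two doses, 6.1.1 adds: "Some analyses of the adverse events will be repeated for Group B using the SAFB if the SAF and the SAFB sets differ".

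The second transplant injection is not certain for every subject. SAP 1.2 describes a first injection "which could be potentially followed 3 to 7 months afterwards by a second injection", and says that subjects who are medically ineligible in that window get no fourth dose in this trial.

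**The concern.** In an interval that opens at Dose 2, only Dose 2 recipients are at risk. Under the default rule, a transplant subject dosed once stays in the denominator and cannot enter the numerator.

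The silence of 6.4.3 is hard to read as an implied at-risk denominator, because the SAP writes one down where it wants one. SAP 6.4.1 uses subjects with diary information in the interval for solicited reactions, and SAP 6.5.3 uses subjects with data at the visit for seroconversion.

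The affected percentage is a primary safety result. Protocol 10.9.3 gives Dose 2 for transplant subjects as a main reason for version 4.0, and Protocol 2.2 expects the data after injection 2 to support the safety rationale for a fourth vaccination. Any error from this denominator runs one way, towards fewer events.

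**Working it through.** The plan states no expected TEAE rate, no sample-size calculation and no hypothesis, so it has no figure of that kind to reproduce. The planned counts are consistent: Protocol 4.1 gives an immunology subset of 36 + 30 + 15 + 48 = 129, of whom 15 are transplant subjects.

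**Inputs**

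- N = transplant subjects in the SAF. The planned maximum is 15 (Protocol 4.1, SAP 1.2).
- m = transplant subjects given Dose 2. The documents do not give it. Assumed range shown: 10 to 15.
- x = Dose 2 recipients with at least one TEAE in the 28 days after Dose 2. Not given; x = 6 is used as an illustration.

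**Step 1: can m be smaller than N?** The documents foresee it. SAP 1.2 provides for medically ineligible subjects. Protocol Table 2, footnotes m and o, makes Dose 2 depend on consent at Visit 6 or Visit 7. Protocol 7.1.1 lists reasons to discontinue IMP in Group B. Protocol 7.2 lists a non-trial SARS-CoV-2 vaccination as a reason for a transplant subject to leave the trial.

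**Step 2: formula.** The SAF percentage is x/N and the at-risk percentage is x/m. Since x/N = (x/m) × (m/N), the relative error of the SAF figure is m/N - 1.

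**Step 3: numbers for N = 15.** The third column assumes a rate of 40% among recipients. The last two columns take x = 6, with exact Clopper-Pearson 95% limits in brackets.

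| m (assumed) | Relative error | SAF figure expected if rate is 40% | x = 6, SAF | x = 6, Dose 2 recipients |
|---|---|---|---|---|
| 15 | 15/15 - 1 = 0% | 40.0% | 40.0% (16.3 to 67.7) | 40.0% (16.3 to 67.7) |
| 14 | 14/15 - 1 = -6.7% | 37.3% | 40.0% (16.3 to 67.7) | 42.9% (17.7 to 71.1) |
| 12 | 12/15 - 1 = -20.0% | 32.0% | 40.0% (16.3 to 67.7) | 50.0% (21.1 to 78.9) |
| 10 | 10/15 - 1 = -33.3% | 26.7% | 40.0% (16.3 to 67.7) | 60.0% (26.2 to 87.8) |

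**Step 4: no events.** With x = 0 the exact upper 95% limit is 1 - 0.025^(1/n). This gives 21.8% for n = 15, 26.5% for n = 12 and 30.8% for n = 10. The SAF would make a null finding look more precise than the number dosed allows.

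**Step 5: does the SAFB repeat settle it?** SAP 6.1.1 commits to repeating some Group B adverse event analyses when the two sets differ. SAP 6.4 treats the repeat as a possibility only. Neither says which tables are meant, so the post-Dose-2 transplant table may or may not be among them.

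**Step 6: the other intervals.** The non-transplant interval, the interval after the first injection and the all-TEAE summary all run from Dose 1. Every SAF subject is at risk from its start, so the SAF is a proper denominator there.

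**The case against.** The strongest reply is that the damage is hypothetical and largely recoverable. The dosing regimen plans two injections for every transplant subject, and if all receive both, the error is zero. SAP 6.1.1 provides for SAFB repeats exactly when the sets differ, which is the only case in which the error can arise. The planned outputs also let a reader rebuild the rate: SAP 6.2 summarises set sizes and lists subjects in the SAF but not the SAFB, 6.1.1 splits tables by transplant status, 6.4.3 gives subject counts beside percentages, and 6.8.1 summarises compliance. No test or decision rule depends on the figure.

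Much of this stands, and it limits the size of the point. It does not remove the point: the rule as written still gives the wrong denominator whenever m is below N, and a primary percentage should not need to be recalculated by its reader.

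Four stronger readings are tempting, and the documents do not support them:

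- That the rate is biased low as a matter of fact. The number given Dose 2 is not stated, so the bias is conditional.
- That all TEAE proportions covering Dose 2 are affected. Only the transplant interval starts there.
- That a two-dose analysis is merely optional. SAP 6.1.1 is firmer than 6.4; the gap is that it names no table.
- That SAFB tables hide the worst Dose 1 events, because Protocol 7.1.1 lets SAEs and safety concerns end dosing. The SAP does not say that SAFB repeats ignore the intervals, and the SAF remains primary, so those events stay in the primary tables.

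**Conclusion.** The point holds for one interval. If any transplant subject in the SAF does not receive Dose 2, the primary TEAE percentage after Dose 2 is understated by the factor m/N, and the plan does not guarantee a corrected figure. At N = 15 each subject who misses Dose 2 takes 1/15 = 6.7% (relative) off the reported rate. The size rests on m, which is an assumption throughout; at m = 15 there is no error. Severity is minor to moderate: the error has one direction and sits in a primary safety endpoint, but the analysis is descriptive, it concerns at most 15 subjects, and neither alpha nor power is involved.

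**What to change.** In SAP 6.4.3, state that percentages for any interval starting at Dose 2 use the number of subjects in the reporting group who received Dose 2 (the SAFB) as denominator, and that intervals starting at Dose 1 keep the SAF.

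In SAP 6.1.1 and 6.4, replace the two differing statements with one: the SAFB is used for the adverse event tables covering the period after Dose 2. Simply striking the hedging words would not do. It would extend the SAFB to all Group B adverse event analyses, including Dose 1 events, where the SAF is the right set.

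The cost is a few sentences and one denominator in the adverse event programs. The downside is that the rates after Dose 2 may look less favourable and any confidence intervals may be wider. If every transplant subject receives Dose 2, the transplant percentages do not change.
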